5.2 EXCLUSION CRITERIA

Participants are excluded from the study if any of the following criteria apply:

Medical conditions

E 01. Participants with immunodeficiency syndromes or other autoimmune diseases requiring immunosuppressive therapy.

E 02. Participants with a history of seizures or epilepsy (history of febrile seizure during childhood is allowed).

E 03. Participants with known clinical relapse (acute or subacute episodes of new or increasing neurological dysfunction followed by full or partial recovery, in absence of fever or infection) within 8 weeks of screening ([1](#)).

- E 04. Participants with a neurological disease history other than MS, eg, head trauma within 3 months, cerebrovascular disease, and vascular dementia.
- E 05. Participants with a history of recent serious infection (eg, pneumonia, septicemia) within 4 weeks of screening; an infection requiring hospitalization or intravenous antibiotics, antivirals, or antifungals within 4 weeks of screening; or chronic bacterial infections (such as tuberculosis) deemed unacceptable, as per Investigator's judgment.
- E 06. Participants who have significant cognitive impairment, psychiatric disease, other neurodegenerative disorders (eg, Parkinson disease or Alzheimer disease), substance abuse (including a history of alcohol abuse), or any other conditions that would make the participants unsuitable for participating in the study or could interfere with assessment or completing the study in the opinion of the Investigator.
- E 07. Participants with a documented history of attempted suicide over the 24 weeks prior to the Screening Visit, presents with suicidal ideation of category 4 or 5 on the Columbia Suicide Severity Rating Scale (C-SSRS), or if in the Investigator's judgment, the participant is at risk for a suicide attempt.
- E 08. Participants with a history of unstable or severe cardiac, pulmonary, oncological, hepatic, or renal disease or another medically significant illness other than MS precluding their safe participation in this study.
- E 09. Participants who received a live vaccine within 14 days before the Screening Visit.
- E 10. Participants with a known history of allergy to any ingredients of SAR443820 (mannitol, lactose monohydrate, sodium starch glycolate, colloidal silicon dioxide, magnesium stearate, hypromellose, titanium dioxide, polyethylene glycol, and microcrystalline cellulose).

Prior/concomitant therapy

- E 11. Participants with a current use of any medications that are moderate or strong inhibitors or strong inducers of CYP3A4 (see Appendix 10 [[Section 10.10](#)]).
- E 12. Participants with a current use of any of the following medications/treatments: fampridine/dalfampridine, ofatumumab, fingolimod, cladribine, siponimod, ponesimod, ozanimod, alemtuzumab, mitoxantrone, ocrelizumab, natalizumab, or similar approved compounds but with different trade names and any unapproved treatments or therapies for MS; any DMTs newly approved after January 2023 that are marketed at any time during the course of the double-blind study period. These medications are not allowed within 5 half-lives before the Screening Visit and for the duration of Part A and Part B.

If the participant has received any of the prohibited medications/treatments, washout will be required according to the table below (no washout is required for permitted medications):

Medication	Exclusionary if used/used within required wash out period
Systemic corticosteroids, adrenocorticotropic hormone	4 weeks prior to the baseline MRI scan
Plasmapheresis, fingolimod, and natalizumab (participants who have discontinued natalizumab in the 24 weeks prior to randomization should be evaluated to rule out PML)	8 weeks prior to randomization
B cell depleting therapies such as ocrelizumab and rituximab	24 weeks prior to randomization or until the return of B cell counts to normal levels, whichever is longer
Alemtuzumab	4 years prior to randomization
Other prohibited MS DMT	5 half-lives or until the end of pharmacodynamics activity, whichever is longer

Abbreviations: DMT = disease-modifying therapy; MRI = magnetic resonance imaging; MS = multiple sclerosis; PML = progressive multifocal leukoencephalopathy

Prior/concurrent clinical study experience

E 13. Participants who have prior/concurrent clinical study enrollment, ie, the participant has taken other investigational drugs within 4 weeks or 5 half-lives, whichever is longer, before the first Screening Visit; concurrent or recent participation in non-interventional studies may be permitted.

Diagnostic assessments

E 14. Participants with a positive human immunodeficiency virus (HIV) antibody test.

E 15. Participants with abnormal laboratory test(s) at the Screening Visit:

- Alanine aminotransferase (ALT) or aspartate aminotransferase (AST) $>3.0 \times$ upper limit of normal (ULN)
- Bilirubin $>1.5 \times$ ULN; unless the participant has documented Gilbert syndrome (isolated bilirubin $>1.5 \times$ ULN is acceptable if bilirubin is fractionated and direct bilirubin $<35\%$)
- Serum albumin <3.5 g/dL
- Estimated glomerular filtration rate <60 mL/min/1.73 m² (Modification of Diet in Renal Disease [MDRD])
- Other abnormal laboratory values or electrocardiogram (ECG) changes that are deemed clinically significant as per Investigator's judgment

E 16. Participants with presence of hepatitis B surface antigen (HBsAg) or anti-hepatitis B core antibodies (HBcAb) at the Screening Visit or within 12 weeks prior to the first dose of study intervention. Serologies consistent with a resolved infection or vaccination, such as the presence of HBsAb, may not exclude potential participants from the trial.

E 17. Participants with positive hepatitis C antibody test result at screening or within 12 weeks prior to starting study intervention. NOTE: participants with a positive hepatitis C antibody due to prior resolved disease can be enrolled, only if a confirmatory negative hepatitis C ribonucleic acid (RNA) test is obtained.

E 18. Participants with a contraindication for MRI, ie, presence of a pacemaker, metallic implants in high-risk areas (ie, artificial heart valves, aneurysm/vessel clips), presence of metallic material (eg, shrapnel) in high-risk areas, known history of allergy to gadolinium, or history of claustrophobia that would prevent completion of all protocol-scheduled MRI.

Note: People with a contraindication to Gd can be enrolled into the study but cannot receive Gd contrast dyes during their MRI scan.

Other exclusions

E 19. Participants who are accommodated in an institution because of a regulatory or legal order; prisoners or participants who are legally institutionalized.

E 20. Participant who are not suitable for participation, whatever the reason, as judged by the Investigator, including medical or clinical conditions, or participants potentially at risk of noncompliance to study procedures.

E 21. Participants who are employees of the clinical study site or other individuals directly involved in the conduct of the study or are immediate family members of such individuals (in conjunction with Section 1.61 of the International Council for Harmonisation of Good Clinical Practice (ICH-GCP) Ordinance E6).

E 22. Participants with any specific situation during study implementation/course that may raise ethics considerations.

E 23. Participants with sensitivity to any of the study interventions, or components thereof, or drug or other allergy that, in the opinion of the Investigator, contraindicates participation in the study.

E 24. Participant is under tutorship or curatorship; participant under safeguard of justice or deprived of his/her liberty by a court decision.

E 25. Participant is unable to provide informed consent.

5.3 LIFESTYLE CONSIDERATIONS

5.3.1 Meals and dietary restrictions

SAR443820 can be administered without regards to meal. Participants should refrain from consuming grapefruit or grapefruit juice (including pomelos, exotic citrus fruits, grapefruit hybrids, or fruit juices) from 5 days before the start of the study intervention until 2 days after the final dose.

5.3.2 Caffeine, alcohol, and tobacco

The information of participant's regular use of alcohol and tobacco should be recorded in the electronic case report form (eCRF). During the entire study, participants should be warned not to

consume substantial quantities of alcohol, defined as >14 grams (1 standard drink) per day in female participants or >28 grams (2 standard drinks) per day in male participants on a regular basis.

5.3.3 Activity

No special restrictions.

5.4 SCREEN FAILURES

A screen failure occurs when a participant who consents to participate in the clinical study is not subsequently randomized. A minimal set of screen failure information is required to ensure transparent reporting of screen failure participants to meet the Consolidated Standards of Reporting Trials (CONSORT) publishing requirements and to respond to queries from regulatory authorities. Minimal information includes demography, screen failure reasons, eligibility criteria, and any serious adverse event (SAE).

Individuals who do not meet the criteria for participation in this study (screen failure) may be rescreened. Rescreening is allowed for participants who fail the initial screening at the Investigator's medical judgment for any manageable reasons that caused the initial screening failure. Participants who fail the initial screening may be rescreened up to 2 times during the study recruitment period. Rescreened participants should be assigned a new identification number and sign a new consent form for every rescreening event.

5.5 CRITERIA FOR TEMPORARILY DELAYING ENROLLMENT/RANDOMIZATION/ADMINISTRATION OF STUDY INTERVENTION

During a regional or national emergency declared by a governmental agency, if the site is unable to adequately follow protocol-mandated procedures, contingency measures are proposed in Appendix 9 ([Section 10.9](#)).

6 STUDY INTERVENTION(S) AND CONCOMITANT THERAPY

Study intervention is defined as any investigational intervention(s), marketed product(s), placebo, or medical device(s) intended to be administered to a study participant according to the study protocol.

6.1 STUDY INTERVENTION(S) ADMINISTERED

Table 4 - Study intervention(s) administered

Intervention label	SAR443820	Placebo
Intervention name	SAR443820	Placebo
Intervention description	Tablet	Tablet
Type	Drug	Drug
Dose formulation	Tablet	Tablet
Unit dose strength(s)	20 mg tablet	0 mg tablet
Dosage level(s)	20 mg once daily	once daily
Route of administration	Oral	Oral
Use	Experimental	Placebo
IMP and NIMP	IMP	IMP
Packaging and labeling	Study intervention will be provided in wallet blister packaging. Each wallet blister packaging will be labeled as required per country requirement.	Study intervention will be provided in wallet blister packaging. Each wallet blister packaging will be labeled as required per country requirement.
Current name	SAR443820	Not Applicable

Abbreviations: IMP = investigational medicinal product; NIMP = non-investigational product

SAR443820 or matching placebo tablets are to be taken once daily. The IMP tablet will be taken orally with water. The IMP should be taken around the same time each day under the same condition (with or without food) throughout the study unless adjustment is specifically requested due to PK sampling at the Day 1, Weeks 2, 6, 12, and 36 site visits.

SAR443820 or placebo may be supplied at the site or from the PI/site/Sponsor to the participant via a Sponsor-approved courier company where allowed by local regulations and agreed upon by the participant.

For a regional or national emergency declared by a governmental agency that results in travel restrictions, confinement, or restricted site access, contingency measures are included in Appendix 9 ([Section 10.9](#)).

6.2 PREPARATION, HANDLING, STORAGE, AND ACCOUNTABILITY

1. The Investigator or designee must confirm appropriate temperature conditions have been maintained during transit for all study intervention received and that any discrepancies are reported and resolved before use of the study intervention.
2. Only participants enrolled in the study may receive study intervention, and only authorized site staff may supply or administer study intervention. All study intervention must be stored in a secure, environmentally controlled, and monitored (manual or automated) area in accordance with the labeled storage conditions with access limited to the Investigator and authorized site staff.
3. The Investigator, institution, or the head of the medical institution (where applicable) is responsible for study intervention accountability, reconciliation, and record maintenance (ie, receipt, reconciliation, and final disposition records).

SAR443820 and placebo tablets require no preparation and will be supplied to the study participants in labeled child-resistant wallets.

Any quality issue noticed with the receipt or use of an IMP (deficiency in condition, appearance, pertaining documentation, labeling, expiration date, etc) must be promptly notified to the Sponsor. Some deficiencies may be recorded through a complaint procedure (see [Section 8.3.10](#)).

A potential defect in the quality of IMP may be subject to initiation of a recall procedure by the Sponsor. In this case, the Investigator will be responsible for promptly addressing any request made by the Sponsor, in order to recall the IMP and eliminate potential hazards.

Under no circumstances will the Investigator supply IMP to a third party (except for direct-to-patient [DTP] shipment, for which a courier company has been approved by the Sponsor), allow the IMP to be used other than as directed by this clinical trial protocol, or dispose of IMP in any other manner.

6.3 MEASURES TO MINIMIZE BIAS: RANDOMIZATION AND BLINDING

- The study will be performed in a double-blind fashion for Part A. The placebo tablet will be identical to the SAR443820 tablet in appearance, quantity, taste, odor, and packaging.
- All participants will be centrally assigned to a randomized study intervention using an interactive response technology (IRT). Before the study is initiated, the login information and directions for the interactive web response system (IWRS) will be provided to each site. The study intervention will be dispensed at the study visits summarized in the SoA. Returned IMP should not be redispensed to participants.
- A randomized participant is defined as a participant from the screened population who has been allocated to a randomized intervention regardless of whether the intervention was received or not. A participant cannot be randomized more than once in the study.
- The randomization will be stratified by MS clinical subtypes (ie, RRMS, SPMS, or PPMS).

- Due to the open-label extension period, a participant assigned to a specific arm at randomization may be allocated, by the IRT, to several (varying) intervention numbers (and corresponding intervention kit numbers) for multiple visits despite having the same intervention arm assignment from randomization. That is, in these cases, the intervention/kit number varies but the arm assignment at randomization does not change.
- The Investigator, site staff, Sponsor monitoring team, and participants will remain blinded to the treatment assignment in Part A until the end of Part B. The Sponsor study team, except Sponsor monitors, will be unblinded after database lock of Part A.
- The bioanalyst and the pharmacokineticist responsible for sample analysis and PK evaluation will be unblinded. However, they will agree not to disclose the randomization schedule or the individual unblinded analytical results before the official opening of the randomization schedule. Preliminary PK data, if needed and available during the study, will refer to means with descriptive statistics, and individual data will not be associated with any individual randomization numbers or participant numbers.
- This is a double-blind study in which participants/care providers/ Investigators/ outcomes assessors, etc. are blinded to study intervention. The IRT will be programmed with blind-breaking instructions. In case of an emergency, the Investigator has the sole responsibility for determining if unblinding of a participant's intervention assignment is warranted (eg, in case of available antidote). Participant safety must always be the first consideration in making such a determination. If the Investigator decides that unblinding is warranted, he/she may, at his/her discretion, contact the Sponsor to discuss the situation prior to unblinding a participant's intervention assignment unless this could delay emergency treatment for the participant. If a participant's intervention assignment is unblinded, the Sponsor must be notified within 24 hours of this occurrence. The date and reason for the unblinding must be recorded.
- For regulatory reporting purposes, and if required by local health authorities, the Sponsor or designee will break the treatment code for all suspected unexpected serious adverse reactions (SUSAR) that are considered by the Investigator or Sponsor to be related to the study intervention.

Methods of blinding

Unless specified otherwise, the baseline brain MRI scan will be used as the reference to assess all MRI-derived endpoints. Standardized endpoint evaluation is assured by central review of brain MRI scans. A blinded MRI central review will be performed for all MRI-derived endpoints. All MRI reviewers will be blinded to treatment assignments and to other participant data. Details on MRI scanning and central review will be described in the central MRI Acquisition and Procedures manual. In addition, in accordance with standard clinical practice, during the blinded intervention period, the Treating Investigator can access MRI reports once a year starting at Month 12, or before if clinically required, through the local radiologist.

A data monitoring committee (DMC) will be used to periodically monitor the safety of this study. Unblinded data will be provided for DMC review by an unblinded independent statistician. Study team members, Investigators, and study participants will not have access to unblinded data.

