8.1.2 Expanded Disability Status Score

The Investigator will perform the EDSS assessment and will be trained and certified to perform the EDSS assessment in a consistent manner. Details regarding the interactive test and certification tool for a standardized, quantified neurological examination and assessment of Kurtzke's FS and EDSS in MS will be provided to Investigators. A Level B qualification will be required for this study. Details regarding the interactive test and certification tool for a

standardized, quantified neurological examination and assessment of Kurtzke's FS and EDSS in MS will be provided to Investigators. A Level B qualification will be required for this study.

The EDSS score will be captured using an electronic EDSS tool. Quality control measures will be put in place to ensure scoring error detection and thus minimize the impact of any scoring and calculation errors.

The Investigator will rate FS in the context of a standard neurological examination and will report these ratings as per the EDSS reporting instructions together with information on the participant's mobility, gait, and use of assistive devices. Standard EDSS assessments of 7 functional domains (visual, brainstem, pyramidal [motor], cerebellar [coordination], sensory, cerebral, and bowel/bladder) scoring will be performed by assessing neurological symptoms in each of these domains. Ambulation scoring will be done to conclude the evaluation. The fatigue evaluation may be optionally recorded, but it will not contribute to assignment of the EDSS score. The total EDSS score will be assigned according to the EDSS scoring rules.

A screening EDSS assessment must be completed to confirm eligibility, and the EDSS assessment must be repeated at the Randomization Visit.

The Investigator will be informed if 12 weeks CDP is observed based on the EDSS data reported in the electronic database. Participants will not be informed of their EDSS scores.

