The MRI scans need to be reviewed by a local radiologist for any non-MS pathology to assure safety reporting as per [Section 1](#). In the event of identification of MRI findings relevant to participant safety, the local radiologist will provide a report to the Investigator. Expected MS findings on MRI scans, not reflecting an acute safety concern for the participant, should not be disclosed to the Treating Investigator or to the site team if not relevant to any safety concern. Any safety concern noted on MRI, whether related to MS or not, shall be provided to the Investigator.

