8.1.4 Multiple sclerosis relapse assessment

8.1.4.1 *Definition of multiple sclerosis relapse*

For the purposes of this study, MS relapse is defined as acute, new neurological symptoms or worsening of previous neurological symptoms with an objective change on neurological examination. Symptoms must be as follows:

1. Be attributable to MS,
2. Last for ≥ 24 hours,
3. Be present at normal body temperature (ie, no infection, excessive exercise, or excessively high ambient temperature), and
4. Be preceded by ≥ 30 days of clinical stability (including no previous MS relapse).

Note: An exacerbation or recurrence of symptoms and signs in a participant with MS that can be reasonably attributed to transient impairment of conduction in previously demyelinated pathways due to drugs (such as rarely occurs a few hours after injections of interferon beta), raised core body temperature (the Uhthoff phenomenon), or systemic cytokine release (such as occurs with the administration of alemtuzumab) will not be considered a relapse.

Refer to [Section 8.3.7](#) for details regarding MS relapse reporting.

8.1.4.2 *Unscheduled assessment visits*

Participants must be instructed to immediately report new neurological symptoms and recurring or worsening of previous symptoms to the Investigator. Any reported symptoms will be collected. If a participant reports symptoms that may be consistent with relapse, an unscheduled assessment visit to the Investigator must be scheduled as soon as possible (whenever possible within 7 days of the onset of the symptoms). The assessment, management, and reporting of MS relapse is made by the Investigator. Diagnosing MS relapses during the study will occur as follows: the Investigator will assess whether the reported episode is consistent with the definition of MS relapse. If it is consistent with the definition of MS relapse or if there is any doubt and the possibility of relapse cannot be ruled out, the standard neurological examination (for the EDSS score) will be performed by the Investigator. If the participant is not referred for EDSS assessment, this will be documented with an explanation of the reason. Whenever possible, the Investigator should perform the EDSS assessment the same day the neurological examination is performed. Subsequent EDSS assessments can still be utilized for confirmation of MS relapses but should be avoided to reduce the risk of changes in participant status between the assessments.

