All MS relapses must be reported on the MS relapse eCRF page. Multiple sclerosis relapse should not be reported as an AE unless, in the judgment of the Investigator, it is unusually severe or medically unexpected, or matches the definition of an SAE.

Safety laboratory tests are optional for the unscheduled assessment visit if no intercurrent disease is suspected. If any intercurrent disease is diagnosed, it will be reported as an AE as per the safety reporting rules.

The participant will be also asked to report possible relapse symptoms during scheduled quarterly visits. If relapse is suspected, the above decision-making and reporting rules apply.

8.1.5 *Timed 25-foot walk test*

As part of the Multiple Sclerosis Functional Composite (MSFC), the T25-FW test is currently the most widely implemented method to objectively quantify gait disability in clinical MS trials. The T25-FW test is developed to quantify changes in gait of MS patients; 1 task is completed, and the amount of time required depends on each patient.

The T25-FW test will be used to assess a participant's walking ability. The participant is directed to one end of a clearly marked 25-foot course and is instructed to walk 25 feet as quickly as safely possible with several repetitions ([25](#), [26](#)). The mean walk time will be used for assessment of the participant's walking ability. An increase of >20% from the baseline score in the T25-FW test is considered as meaningful worsening ([27](#)). The Examining Investigator/rater will perform this test.

8.1.6 9-Hole Peg Test

The 9-HPT will be used to assess a participant's manual dexterity and fine motor skills. This is a PerfRO tool (performance outcome). A participant will be asked to place pegs into holes and remove them with the dominant and non-dominant hand for several repetitions (26). The mean time to test completion will serve as an assessment of the participant's hand dexterity. An increase of >20% from the baseline score in the 9-HPT is considered meaningful worsening (27). The Examining Investigator/rater will perform this test.

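### Protocol 6.3 and 8.1.3 conflict on whether the Treating Investigator may see MS findings on MRI, and nothing keeps those findings from whoever rates EDSS and relapse

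*Protocol*

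**What the plan says.** **Access.** Protocol 6.3 (Methods of blinding) states that, while treatment is blinded, "the Treating Investigator can access MRI reports once a year starting at Month 12, or before if clinically required, through the local radiologist". Content is not restricted.

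**Non-disclosure.** Protocol 8.1.3 covers "Expected MS findings on MRI scans, not reflecting an acute safety concern for the participant" and says that these "should not be disclosed to the Treating Investigator or to the site team if not relevant to any safety concern". The same paragraph keeps a safety channel open: "Any safety concern noted on MRI, whether related to MS or not, shall be provided to the Investigator".

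**Who rates.** For EDSS (8.1.2): "The Investigator will perform the EDSS assessment and will be trained and certified". For relapse (8.1.4.2): "The assessment, management, and reporting of MS relapse is made by the Investigator". For T25-FW and 9-HPT (8.1.5 and 8.1.6): "The Examining Investigator/rater will perform this test". The terms Treating Investigator and Examining Investigator/rater are not defined anywhere.

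**Scope of the local read.** Section 8.1.3 limits the local radiologist's review to pathology other than MS. Section 8.3.8 asks for local review for pathology of any kind.

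**Blinding in Part B.** Under 6.3 the Investigator, site staff, monitoring team and participants "will remain blinded to the treatment assignment in Part A until the end of Part B". SAP 3.1 compares Part B efficacy by the arm randomised in Part A.

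**The concern.** Both rules are current, name the same role and concern the same scans. One opens MRI reports to the Treating Investigator on a yearly schedule. The other withholds the MS content of those scans. Two sites could act differently and each be following the protocol.

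This matters because EDSS scoring and relapse calls involve judgement. Time to 12-week confirmed disability progression is one of the main secondary endpoints in the synopsis, and annualized relapse rate is also secondary. A rater who knows that a participant has new lesions may be readier to score a worsening or accept an episode as a relapse. If lesion activity differs between arms, that expectation acts unequally on the arms, even though nobody has learned the treatment assignment.

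**Working it through.** The plan states no figure to reproduce here. The check is a comparison of passages plus a timing calculation.

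**1. Can the two rules be read as one?**
- If 6.3 covered only safety findings it would add nothing, because 8.1.3 already releases every safety concern, whether or not MS-related. A yearly schedule is also not a safety trigger.
- If 6.3 is an exception to 8.1.3, MS findings do reach the Treating Investigator.
- If 8.1.3 governs what a report released under 6.3 may contain, MS findings do not reach that person.

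There is no cross-reference to choose between the last two readings, and they have opposite consequences for the rater.

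**2. Is the reader of the report kept apart from the rater?** The protection runs one way. Under 6.3 and 8.1.3, central MRI reviewers are blinded to treatment and to other participant data. No matching rule keeps EDSS or relapse raters from MRI reports. Section 6.3 lists outcomes assessors as blinded, but to study intervention. The Examining role is named only for the walk and peg tests.

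**3. When could exposure occur?**
- End of Part A: 48 × 7 = Day 336, and 336 / 30.44 ≈ 11.0 calendar months.
- Calendar Month 12: 12 × 30.44 ≈ Day 365, and 365 / 7 ≈ Week 52, after Part A.
- Study months of four weeks: 12 × 4 = Week 48. Protocol 8.1.2.1 pairs 12 and 24 weeks with 3 and 6 months, SAP 3.3.1 equates 6 months with 24 weeks, and Protocol 2.3.3 describes treatment as lasting 12 months.

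| Period | Route under 6.3 |
|---|---|
| Before Week 48 | Clinically required route only; the trigger is not defined |
| Week 48 visit | Also the yearly route, if Month 12 means this visit |
| Part B | Both routes |

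EDSS and MRI are both scheduled at Week 48, with no stated order between rating and opening a report. The protocol does set an order elsewhere: SoA footnote q for Part A has MSIS-29v2 and MSWS-12 completed before health status is discussed or other tests are done.

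**4. Does Part B exposure matter when treatment is open-label?** Yes. SAP 3.3.2 gives a hazard ratio and p-value by randomised arm for 24-week confirmed disability progression, and analyses relapse rate from randomization to Week 96.

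**5. Can a size be given?** Write the distortion in a confirmed-event proportion as (L_P − L_S) × b × r × d. Here L_P and L_S are the proportions with new lesions reported on placebo and SAR443820, b is the share with a borderline score, r is the share whose rater read the report, and d is the shift in confirmation probability that reading causes. This simple form takes b, r and d as equal in both arms. The documents give none of these five quantities, so no value follows. The distortion is zero if lesion activity is equal in the arms or if raters never open reports.

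**The case against.** The best defence is that the passages fit together: 8.1.3 sets the default for what the radiologist passes on, and 6.3 grants a limited clinical exception. Amendment 01 added the early-access clause on purpose. Section 8.1.3 is also conditional and says should not, so calling it a flat ban would overstate it. This shows that some access was intended. It does not remove the problem, because an exception of that kind is exactly what lets lesion findings reach a rater.

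Second, the local report may contain no lesion results, since 8.1.3 confines the local read to non-MS pathology. That is possible, but 8.3.8 sets a wider scope and 6.3 sets none. The content of the report is therefore unsettled in both directions.

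Third, EDSS raters are certified, and scoring uses an electronic tool with quality control. These measures reduce scoring error. They do not address expectation.

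Some stronger readings are tempting but not supported:
- **The rater and the report reader are the same person.** This is an inference from undefined roles. The documents allow it but do not state it.
- **Month 12 is the Week 48 visit.** The protocol's own conversions make this plausible, but it is not established.
- **One third of Part A progression events are exposed**, because onsets at Weeks 12, 24 and 36 can be confirmed and only the last depends on Week 48. That needs onsets spread evenly, Month 12 to mean Week 48, and reports opened before the EDSS. None of these is given.
- **All Part B ratings are exposed.** Access is permitted, not required.

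**Conclusion.** The conflict stands and should be resolved. As written, a site can comply with 6.3 and still place lesion findings before the person who rates EDSS or judges relapse, and the plan requires no record that this happened.

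The consequence is possible assessor bias in EDSS-based progression and relapse rate. It depends on three conditions: the report contains MS lesion findings, the rater opens it, and lesion activity differs by arm. No size can be derived from the documents. A reader might infer that the trial is unblinded or that the main result is at risk. The documents do not support that: seeing lesions does not reveal the assignment, sNfL is a laboratory measurement, and MRI endpoints are read centrally by blinded reviewers. The point is a correction to the protection of subjective secondary endpoints.

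**What to change.** Reconcile Protocol 6.3, 8.1.3 and 8.3.8 into one rule:

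1. Make routine access under 6.3 (neither safety-related nor clinically required) subject to the 8.1.3 non-disclosure of expected MS findings, for anyone who rates EDSS or judges relapse.
2. Where a report is opened, require that visit's EDSS, T25-FW, 9-HPT and relapse assessments to be entered first, and record the access date.
3. Define the Treating and Examining roles, say what Month 12 means, and give the local read one scope.
4. Leave the release of safety-relevant findings unchanged. The scope of the clinically required route is for the sponsor to reconcile with 8.1.3.

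Item 2 alone protects only the visit in question, because a report opened after one rating is still known at the next. Item 1 is therefore needed as well. Exposure through the clinically required route would remain, but the recorded dates would show which ratings followed it.

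The cost is a short protocol edit, a note to local radiologists and one date field. The downside is that routine non-safety MRI findings reach raters later, or not until their ratings are complete.
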